9.3 Variables

9.3.1 Exposure definition

As exposure, we will assess prescriptions of phenprocoumon and NOACs, i.e. rivaroxaban (15 mg or 20 mg once daily), apixaban (2.5 mg or 5 mg twice daily), edoxaban (30 mg or 60 mg once daily). All prescriptions will be assessed based on the documented dispensation date. A detailed list of products with the corresponding central pharmaceutical number (CPN) of the study drugs is displayed in Annex 3: Additional information.

Each patient will be assigned to one of the four exposure groups based on the index drug: new users of phenprocoumon, rivaroxaban, apixaban or edoxaban.

Exposure time for phenprocoumon and NOACs starts on the index date and will be calculated as the sum of days of supply + a grace period of 14 days (in case of treatment discontinuation). A gap period of 30 days between the estimated end of supply and any following prescription of the index drug is allowed.

Since NOACs are prescribed in a fixed dose, the days of supply corresponds to the number of tablets in a dispensed package for rivaroxaban and edoxaban (used once daily) or half the number of tablets in a package for apixaban (used twice daily).

As of an international normalized ratio (INR) between 2 and 3, phenprocoumon patients are often asked to titrate or change their daily doses. Therefore, the exposure time calculation for phenprocoumon is not straightforward . In an anonymous empirical data collection using phenprocoumon diaries of anticoagulated NVAF patients in the university medical center of Schleswig-Holstein information on phenprocoumon dosing will be collected. The results of this survey will be used to calculate a median daily dose which will then be used as the basis for the phenprocoumon exposure time in this study.

As a sensitivity analysis, to account for the intra- and interpersonal variability of phenprocoumon treatment, a personalized defined daily dose (pDDD) based on the observed phenprocoumon prescriptions for each patient in the InGef database will be calculated. For this purpose, amount of active ingredient (AAI) dispensed to each patient of the phenprocoumon group will be obtained for each prescription. A prescribed personalized daily dose (pPDD) representing the average daily dose taken during follow-up will be computed for each patient i such that:

$$pPDD_{i} = \frac{\sum_{k=1}^{K-1} AAI_{i,k}}{T_{i}}$$

- $k = \text{index of the prescriptions received during follow-up } (k \in \{1, K\}).$
- T= number of days between the first and the last prescription during follow-up

For the sake of simplicity, only prescriptions of patients who were solely treated with phenprocoumon during follow-up will be included in the computation of the empirical DDD (eDDD). Patients with a pDDD below the 5th or above the 95th percentile and patients with only one prescription for phenprocoumon will be assigned the median pDDD (=eDDD) over all patients.

The exposure time (ET) corrected from the intra- and interpersonal variability of phenprocoumon treatments can be computed for each patient i as:

$$ET_i = \frac{\sum_{k=1}^{K} AAI_{i,k}}{pDDD}$$

Patients will be considered as having discontinued treatment with the index drug, if they did not receive a subsequent prescription of the respective drug between the last prescription and a gap period of 30 days.

Patients will be considered as having switched from the index drug to phenprocoumon or another NOAC if they received a prescription of the respective drug during continuous exposure time to the index drug as described above. The date of the first prescription of phenprocoumon or another

NOAC will be defined as the date of treatment switch at which patients will be censored. For the comparison of the effectiveness outcomes in patients receiving reduced vs. standard doses of NOACs (other objectives), patients will also be censored if they switch from reduced to standard dose or vice versa.

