9.4 Data sources

This study will be conducted based on the InGef (former HRI) database which is an anonymized healthcare claims database covering all geographic regions of Germany. It includes longitudinal data from approx. 6.7 million Germans insured in one of approx. 64 German SHIs currently contributing data to the database (mainly company or guild health insurances).

Claims data are transferred directly from health care providers to a specialized data center owned by SHIs, which provides data warehouse and IT services. In the data center (acting as a trust center), data is anonymized before entering the InGef database. Data are anonymized with respect to individual insured members, health care providers (e.g. physicians, practices, hospitals, pharmacies), and the respective SHI. The most important data elements included in the database are displayed in Table 2. The time period covered by the database is limited to a look-back period of 6 years starting with the most current complete year of data (11).

Table 2 Information included	in the InGef Database
-------------------------------------	-----------------------

Demographics

Gender

Age

Date of death

	Region for place of living				
	Insurance status (e.g. retired, family insurance)				
	Date of insurance start and end (observation period)				
Outpatient Care	Diagnosis (ICD 10-GM Codes) and quarter in which the diagnosis was documented				
	Procedures performed (e.g. laboratory, radiology, echocardiography) (EBM-Codes) and day of performance				
	Type of specialist that documented the diagnosis and performed the procedure (e.g. cardiologist, general practitioner)				
	Costs of outpatient care				
Pharmacy	Drug dispensed by central pharmaceutical number (package level) – this is mapped to ATC codes and DDD's by InGef				
	Quantity dispensed				
	Day of prescription				
	Day of dispensing				
	Type of doctor prescribing (e.g. cardiologist, general practitioner)				
	Costs of drugs dispensed from SHI perspective (without individual rebates between single sickness funds and pharmaceutical companies)				
Hospital care	Main diagnosis (ICD 10-GM Codes) and additional diagnoses				
	Performed procedures and surgeries (e.g. pacemaker implant, implantable cardioverter defibrillator				
	Date of hospital admission				
	Reason for admission (e.g. accident, emergency, normal)				
	Date of end of hospital stay				
	Reason of end of hospital stay (e.g. death in hospital, normal end)				

	DRG-Code			

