Where $\overline{X_T}$, S_T^2 and $\overline{X_C}$, S_C^2 denote the weighted sample mean and weighted sample variance of the variable in the treated and control patients, respectively. For binary variables, the SMD is calculated by

$$SMD_{cat} = \frac{100(P_T - P_C)}{\sqrt{(P_T(1 - P_T) + P_C(1 - P_C))/2}},$$

Where P_T and P_C denote the weighted sample prevalence of the variable in the treated and control patients, respectively.

In a third step, we will additionally conduct a propensity score matched analyses for each comparison. A 1:1 matching will be performed using the nearest-neighbor approach with a caliper of 0.2 without replacement. Again, the balance of patient characteristics between treatment groups will be checked in analogy to the description above.

For the analysis of IS /SE as combined endpoint and ICH (primary objectives) as well as for the comparison of reduced vs. standard dose of NOACs (other objectives) all three approaches will be used, i.e. Cox proportional hazards regression models, IPTW and propensity-score matching. For all other analyses (secondary objectives) only Cox proportional hazards regression models and IPTW will be applied.

To describe the risk of recurrent hospitalizations and IS/ SE, the following analyses will be conducted. Analyses of recurrent events will be conducted for the unadjusted, matched as well as IPTW populations:

1) Mean cumulative function (MCF)

An important quantity is the mean number of recurrent events per subject by a certain time, i.e. the mean cumulative function (MCF) which is defined as

$$\mu(t) = E(N(t)).$$

The MCF is a marginal quantity, i.e. independent of the history of the event process. The common Nelson-Aalen estimator for survival analysis can be used as a non-parametric estimator for the MCF under the assumption of independent censoring, i.e. patients remaining are representative of the population.

Let $Y_i(t)$ indicate whether patient i = 1, ..., m is "at risk" for an event at time t and $Y_{\Sigma}(t) = \sum_{i=1}^{m} Y_i(t)$ the total number of patients at risk at time t. With $dN_{\Sigma}(t) = \sum_{i=1}^{m} Y_i(t)dN_i(t)$ being the total number of events at time t and H distinct event times across all m patients denoted as $t_1 \leq \cdots \leq t_H$ the Nelson-Aalen estimator is given as

 $\hat{\mu}(t) = \sum_{h:t_h \le t} \frac{dN_{\Sigma}(t_h)}{Y_{\Sigma}(t_h)}.$

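### Inpatient days are not credited to drug supply, so long stays, or shorter stays with late refills, can be misread as discontinuation, chiefly in the persistence and recurrent-event analyses

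*Protocol*

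**What the plan says.** Section 9.3.1 sets the exposure rule for all four groups: "Exposure time for phenprocoumon and NOACs starts on the index date and will be calculated as the sum of days of supply", plus "a grace period of 14 days (in case of treatment discontinuation"). It adds: "A gap period of 30 days between the estimated end of supply and any following prescription of the index drug is allowed". For NOACs, days of supply come from the tablet count of the dispensed pack. For phenprocoumon they come from a median daily dose. No term refers to time in hospital.

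Section 9.4 (Table 2) places drug information in the Pharmacy block, beginning with "Drug dispensed by central pharmaceutical number (package level"). The Hospital care block lists diagnoses, procedures, the admission date and "Date of end of hospital stay", but no drug field.

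Section 9.2.3 ends follow-up in the main analysis at the first outcome event, discontinuation or another listed reason. It says that specific analyses may differ as set out in 9.3.1, but 9.3.1 gives no separate rule for recurrent events. Section 9.3.2 dates events identified from hospital diagnoses to admission. For the mean cumulative function, section 9.7.2 relies on the Nelson-Aalen estimator "under the assumption of independent censoring, i.e. patients remaining are representative of the population".

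A side point: section 9.3.1 later words the discontinuation window as running "between the last prescription and a gap period of 30 days", which is a different starting point from the end of supply. The two sentences must be reconciled. The check below uses the end of supply.

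**The concern.** A patient in hospital for several days probably does not use the home pack. The pack then lasts that much longer and the next dispensing is delayed by the same number of days. The rule treats those days as home consumption, so the delay looks like a lapse in treatment.

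Three kinds of analysis are exposed to this, to different degrees.

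- **Persistence.** Discontinuation is the event, with a hazard ratio and risks at months 3 to 24. A stay can create an event that did not happen.
- **Recurrent hospitalization and recurrent IS/SE.** The stay for one event can end observation before the next. Censoring then depends on event history, and the patients who remain no longer represent the population. If patients with long stays are also the ones readmitted most, the mean number of events is understated.
- **First IS/SE and first ICH.** A stay for some other cause, before the outcome, can end follow-up early. The propensity weights use baseline characteristics only and cannot correct for that.

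Section 9.9 discusses drug that was dispensed but not taken. It does not mention drug taken in hospital that never appears as a dispensing.

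**Working it through.** **No figure of the plan to reproduce.** The protocol gives no length of stay, refill lateness or rate of false discontinuation. The only fixed input is the 30-day gap in 9.3.1. Everything else below is an assumption, shown as a range.

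**Step 1. The condition.** Let H be the inpatient days inside one supply interval, with no home tablets used, and D the patient's usual lateness in refilling after running out. The apparent gap is H + D. A persistent patient is misread as discontinued when H + D > 30.

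**Step 2. Shortest stay that breaks the gap (31 − D).**

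| Usual lateness D (days) | Inpatient days needed |
|---|---|
| 0 | 31 |
| 7 | 24 |
| 14 | 17 |
| 21 | 10 |
| 28 | 3 |

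**Step 3. Probability that one stay triggers false discontinuation.** D is assumed to lie between 0 and 30.

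- D uniform on 0 to 30: P = H/30.
- D exponential with mean m, truncated at 30: P = [exp(−(30−H)/m) − exp(−30/m)] / [1 − exp(−30/m)].

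Examples: for m = 5 and H = 5, (0.00674 − 0.00248)/0.99752 = 0.4%. For m = 10 and H = 20, (0.3679 − 0.0498)/0.9502 = 33.5%.

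| Assumed lateness | 5-day stay | 10-day stay | 20-day stay |
|---|---|---|---|
| Uniform, 0 to 30 days | 16.7% | 33.3% | 66.7% |
| Exponential, mean 10 days | 3.4% | 9.0% | 33.5% |
| Exponential, mean 5 days | 0.4% | 1.6% | 13.3% |

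These figures are conditional on a stay. Early refills make D negative and lower all of them: a patient who usually refills 14 days early needs more than 30 + 14 = 44 inpatient days.

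**Step 4. Per patient over a year.** A simulation assumed a 98-day pack, one admission per year on average, exponentially distributed stays, a fixed lateness and one year of follow-up.

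| Mean stay (days) | D = 0 | D = 14 | D = 21 |
|---|---|---|---|
| 7 | 1.6% | 8.6% | 14.3% |
| 10 | 4.4% | 15.8% | 20.3% |
| 20 | 18.2% | 32.1% | 31.0% |

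The entries are the share of adherent patients falsely discontinued. Admissions lost to a recurrent-hospitalization analysis ran from 0.8% to 16.0% over the same scenarios. With inpatient days credited, false discontinuation was 0% in every scenario.

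**Step 5. Possible difference between arms.** Phenprocoumon supply rests on one median daily dose, so a patient taking less looks late without being late. With an assumed 98-day supply, a patient at 90% of the median has 98/0.9 − 98 = 10.9 days of apparent lateness, and a 20-day stay breaks the gap. At 80% it is 98/0.8 − 98 = 24.5 days, and a 6-day stay does. This shows that a difference is possible, not how large it is.

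**Step 6. Do the sensitivity analyses cover it?** Section 9.7.3 has three. Stockpiling credits early refills only. Excluding patients with prior events is unrelated. The pDDD analysis divides by calendar days between prescriptions, so it absorbs inpatient days indirectly, but only for phenprocoumon and only for IS/SE and ICH.

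**The case against.** The strongest case against has five parts.

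- **Primary outcomes.** A reader might infer that the primary outcome censors itself. The protocol does not support that. An event admitted while the patient counts as exposed is counted at admission, and follow-up ends there, so its own stay cannot remove it. This objection stands.
- **The gap already absorbs most stays.** A reader might infer that adherent patients in general are pushed out, or that any stay over 30 days is certain to do it. Neither holds. An on-time refiller needs 31 inpatient days in one supply interval, and an early refiller needs more. This stands too.
- **Unstated premises.** Table 2 is introduced with "The most important data elements included in the database are displayed in Table 2", so the absence of inpatient medication from the database is an inference, and hospital supply during a stay is stated nowhere. Both are assumptions here. Section 9.3.1 nevertheless assesses every prescription by dispensing date, so the stated rule would not use inpatient drug data even if they existed.
- **Left to the SAP.** Section 9.7.3 announces a more detailed SAP, which could add a bridging rule. But the protocol does not leave exposure time open. It states the formula, and the formula has no such term.
- **The remedy trades one error for another.** Bridging counts unobserved days as exposed, although the drug may have been stopped or replaced in hospital. That is fair, and it is why both versions should be reported. The error is bounded by the length of the stay.

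**Conclusion.** The point holds in a limited form. The rule in 9.3.1 can read a long stay, or a shorter stay combined with a late refill, as discontinuation. The main damage is to secondary objectives: false events in persistence, and event-dependent censoring in the two recurrent-event analyses. For first IS/SE and first ICH, the effect is confined to earlier stays for other causes, and its size was not estimated.

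The size is not determined by the protocol. Under non-negative lateness, 0.4% to 17% of 5-day stays and 13% to 67% of 20-day stays would be misread, and fewer with early refills. The conclusion assumes that the hospital supplies the drug, that home tablets are not used during the stay, and that discontinuation also ends follow-up in the recurrent-event analyses, which the protocol does not say outright.

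A reader might also infer a bias in the hazard ratios towards one drug. Nothing in the protocol establishes that. Section 7 does show that exposure rules can matter: in the earlier renal-impairment analysis, changing only the phenprocoumon exposure definition moved its mean follow-up for ischaemic stroke from 219.56 to 415.4 days and the hazard ratio from 0.84 to 1.02. That comparison does not measure hospital days.

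**What to change.** In section 9.3.1, extend the estimated end of supply by the inpatient days, from admission to discharge, that fall within a supply interval. Apply this in all four exposure groups. Use the extended date for exposure time, the 30-day gap and discontinuation, at least in the persistence, recurrent hospitalization and recurrent IS/SE analyses. Report first IS/SE and first ICH with and without the extension. State in the same place whether discontinuation ends follow-up in the recurrent-event analyses, and add the inpatient-supply assumption to section 9.9.

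The cost is a sentence or two of protocol text and a few lines of code, since the dates are already held. The downside is that if the drug was stopped in hospital, up to the length of that stay is counted as exposed.

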9.2.3 Exclusion criteria

Patients meeting any of the following exclusion criteria (see Annex 3: Additional information) will be excluded from the analysis:

• A verified ambulatory or primary/ secondary hospital discharge diagnosis of valvular atrial fibrillation in the baseline period;

- A verified ambulatory or primary/ secondary hospital discharge diagnosis indicating pregnancy in the baseline period;
- A verified ambulatory or primary/ secondary hospital discharge diagnosis of a transient cause of atrial fibrillation in the baseline period;
- A verified ambulatory or primary/ secondary hospital discharge diagnosis of venous thromboembolism (VTE) in the previous or same quarter of the index date;
- A claim for hip or knee replacement surgery in the 60 days prior to or on the index date;
- A prescription of heparin or fondaparinux in the 60 days prior to or on the index date;
- A prescription of more than one oral anticoagulant (rivaroxaban, apixaban, edoxaban or phenprocoumon) on the index date;
- A prescription of warfarin or dabigatran in the baseline period or on the index date;
- A verified ambulatory or primary/ secondary hospital discharge diagnosis of end-stage kidney disease or a claim for dialysis in the baseline period;
- Patients receiving an initial dose of rivaroxaban 10 mg/ 2.5 mg or edoxaban 15 mg (these dosages are not indicated for the treatment of NVAF).
- A prescription of contraindicated drug for apixaban or rivaroxaban due to drug interactions (i.e. azole antifungals and HIV protease inhibitors) in the 60 days before or on the index date.

For the main analysis, patients will be followed from the index date until the first diagnosis of the respective outcome event, discontinuation of the index drug, death, end of continuous insurance in the SHI or the end of the study period (31 December 2017), whichever comes first. Patients will be censored in all analyses if they switch to phenprocoumon or another NOAC (including dabigatran), receive a prescription of heparin/ fondaparinux, warfarin, rivaroxaban 10 mg/ 2.5 mg, edoxaban 15mg or a contraindicated drug as defined above. For specific analyses, the end of follow-up may differ as described in 9.3.1.

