9.7.2 Main analysis

Analyses will be conducted in line with good statistical practices. Models will use confounding factors to adjust for group differences. However, unmeasured confounding and resulting confounding bias affecting point estimates, confidence intervals and any p-values in the treatment group comparisons may remain.

In a first step, Cox proportional hazards regression models will be applied in in each treatment group compared to phenprocoumon (reference) to estimate crude and confounder adjusted hazard ratios (HRs) of the above mentioned outcomes as well as treatment discontinuation (persistence) with accompanying 95% confidence intervals and *p*-values. Persistence (risk of non-persistence) will also be calculated separately for specific time points of interest (months 3, 6, 9, 12, 18 and 24). In the analysis of reduced vs. standard dose of NOACs, the standard dose will be used as reference. Kaplan-Meier cumulative incidence plots will be generated to characterize risk of outcome events of interest over time.

Information on confounding factors which are planned to be included in the models as well as in the estimation of the propensity score can be found in section 9.3.3.

In a second step, we will use the stabilized inverse probability of treatment weighting (IPTW) approach based on the propensity score to adjust for potential confounding resulting from imbalances in the baseline characteristics of different treatment groups. The objective of IPTW

based analysis is to create a weighted sample, for which the distribution of possible confounding variables is approximately the same between comparison groups (12,13). The propensity score is defined as the patient's probability to receive a treatment under investigation (i.e. phenprocoumon for main analyses and standard dose for the analyses of reduced vs. standard dose of NOACs) given a set of known patient's baseline characteristics. Propensity scores will be calculated using multiple logistic regression on a relevant set of patient characteristics listed in section 9.3.1 for each 1:1 comparison separately, e.g. rivaroxaban vs. phenprocoumon, rivaroxaban 15 mg vs. rivaroxaban 20 mg etc.

Let Z be an indicator variable relating to the treatment received by a patient, Z = 1 for an active treatment (e.g. rivaroxaban), Z = 0 for a control treatment (warfarin), and let X denote a vector of observed patient baseline characteristics. Then the propensity score is e = P(Z = 1|X). The inverse

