Rivaroxaban	13502499	Xarelto 15 mg Medico	Reduced
Rivaroxaban	13502507	Xarelto 20 mg Medico	Standard
Rivaroxaban	13711866	Xarelto 15 mg Abacus	Reduced
Rivaroxaban	13721818	Xarelto 15 mg Abacus	Reduced
Rivaroxaban	13721830	Xarelto 20 mg Abacus	Standard
Apixaban	1647755	Eliquis 5 mg	Standard
Apixaban	1647778	Eliquis 5 mg	Standard
Apixaban	1647784	Eliquis 5 mg	Standard
Apixaban	1647809	Eliquis 5 mg	Standard
Apixaban	1647821	Eliquis 5 mg 5x20	Standard
Apixaban	3643804	Eliquis 2,5 mg CC Ph.	Reduced
Apixaban	04700504	Eliquis 2,5 mg Emra	Reduced
Apixaban	04700510	Eliquis 2,5 mg Emra	Reduced
Apixaban	04700527	Eliquis 2,5 mg Emra	Reduced
Apixaban	04712163	Eliquis 2,5 mg Kohl Ph.	Reduced
Apixaban	04712186	Eliquis 2,5 mg Kohl Ph.	Reduced
Apixaban	05117273	Eliquis 5 mg Eurim	Standard
Apixaban	08400012	Eliquis 2,5 mg	Reduced
	Rivaroxaban Apixaban	Rivaroxaban 12645535 Rivaroxaban 12868703 Rivaroxaban 13155164 Rivaroxaban 13131135 Rivaroxaban 13331135 Rivaroxaban 13331141 Rivaroxaban 13502499 Rivaroxaban 13502507 Rivaroxaban 13711866 Rivaroxaban 13721818 Rivaroxaban 13721830 Apixaban 1647755 Apixaban 1647784 Apixaban 1647784 Apixaban 1647821 Apixaban 1647809 Apixaban 04700504 Apixaban 04700510 Apixaban 04712163 Apixaban 04712186	Rivaroxaban12645535Xarelto 20 mg OrifarmRivaroxaban12868703Xarelto 20 mg AbacusRivaroxaban13155164Xarelto 20 mg ADL Ph.Rivaroxaban13331135Xarelto 15 mg 2CareRivaroxaban13331141Xarelto 20 mg ADL Ph.Rivaroxaban13331141Xarelto 20 mg 2CareRivaroxaban13502499Xarelto 15 mg MedicoRivaroxaban13502507Xarelto 20 mg MedicoRivaroxaban13711866Xarelto 15 mg AbacusRivaroxaban13721818Xarelto 20 mg AbacusRivaroxaban13721830Xarelto 20 mg AbacusApixaban1647755Eliquis 5 mgApixaban1647784Eliquis 5 mgApixaban1647809Eliquis 5 mgApixaban1647801Eliquis 5 mg CC Ph.Apixaban04700504Eliquis 2,5 mg EmraApixaban04700510Eliquis 2,5 mg EmraApixaban04712163Eliquis 2,5 mg Kohl Ph.Apixaban04712186Eliquis 2,5 mg Kohl Ph.Apixaban04712186Eliquis 2,5 mg Kohl Ph.

B01AF02	Apixaban	08400029	Eliquis 2,5 mg	Reduced
B01AF02	Apixaban	08400035	Eliquis 2,5 mg	Reduced
B01AF02	Apixaban	08400041	Eliquis 2,5 mg	Reduced
B01AF02	Apixaban	10218496	Eliquis 5 mg Kohl Ph.	Standard
B01AF02	Apixaban	10232906	Eliquis 5 mg CC Ph.	Standard
B01AF02	Apixaban	10250465	Eliquis 2,5 mg Filmtabletten	Reduced
B01AF02	Apixaban	10273130	Eliquis 5 mg Eurim	Standard
B01AF02	Apixaban	11174884	Eliquis 5 mg Emra	Standard
B01AF02	Apixaban	11341537	Eliquis 2,5 mg Filmtabletten Docpharm	Reduced

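### At-risk time in days 15 to 30 after the end of supply depends on whether the patient later refills, and the discontinuation sentence starts its 30-day clock at a different point

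*Protocol*

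**What the plan says.** Protocol Section 9.3.1 has three rules on when exposure ends.

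- **Tail for stoppers.** Exposure is the "sum of days of supply + a grace period of 14 days (in case of treatment discontinuation").
- **Gap for refillers.** "A gap period of 30 days between the estimated end of supply and any following prescription of the index drug is allowed".
- **Discontinuation.** Patients have discontinued "if they did not receive a subsequent prescription of the respective drug between the last prescription and a gap period of 30 days". The end of supply is not mentioned here.

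These rules reach most of the analysis. Under Section 9.2.3, "patients will be followed from the index date until the first diagnosis of the respective outcome event, discontinuation of the index drug, death" or a later administrative end. Section 9.3.1 counts a switch only "if they received a prescription of the respective drug during continuous exposure time to the index drug". Section 9.7.2 also analyses "treatment discontinuation (persistence") as an outcome, with hazard ratios and estimates at months 3 to 24.

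The three sensitivity analyses in Section 9.7.3 concern stockpiling, prior outcome events and the phenprocoumon daily dose. None varies the 14 or the 30 days.

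**The concern.** There are two separate problems.

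**Follow-up conditioned on the future.** Whether a patient is at risk on day 20 after supply runs out should be decidable on day 20. Under the first two rules it is settled only once it is known whether a refill comes by day 30. An outcome in that interval can itself prevent the refill. Fatal bleeding, and severe ischaemic stroke defined through in-hospital death (Section 9.3.2), are the clearest cases. Such events drop out of the numerator, while days 15 to 30 of patients who stay well and refill remain in the denominator.

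**Two starting points for the 30 days.** One sentence counts from the estimated end of supply and the other from the last prescription. The second is the only sentence that defines discontinuation, so the ambiguity bears directly on the persistence outcome and on the end of follow-up for both primary outcomes.

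**Working it through.** The protocol gives no figure for the effect of these rules, so there is none to reproduce. The check applies the wording to cases and then sizes the effect under stated assumptions.

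**1. Same history, different status.** Two patients have the same supply. On day 20 after it ends, both are event-free and have not refilled. The first refills on day 25, inside the 30-day gap, so day 20 is exposed time. The second never refills, so exposure ended on day 14. Only later information separates them.

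**2. Two clocks.** Let S be days of supply and g the days from end of supply to refill. Counted from end of supply, treatment continues if g ≤ 30. Counted literally from the last prescription, it continues only if S + g ≤ 30.

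| S | g | Refill on day S + g | From end of supply | From last prescription |
|---|---|---|---|---|
| 28 | 0 | 28 | continues | continues |
| 28 | 14 | 42 | continues | discontinued |
| 50 | 0 | 50 | continues | discontinued |
| 98 | 0 | 98 | continues | discontinued |

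S = 50 is apixaban: Section 9.3.1 sets its supply at "half the number of tablets in a package for apixaban (used twice daily"), and Annex 3 lists "Eliquis 5 mg 5x20". If that means 5 × 20 = 100 tablets (an assumption), then 100 / 2 = 50 days.

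**3. Size of the conditioning bias.** None of these inputs is in the protocol: S = 98 days, stopping probability p = 0.08 per refill, exponential refill gaps with mean m = 10 days, constant event hazard, and a probability q of 0.3 to 0.9 that an event in days 15 to 30 prevents the refill. Per dispensing cycle:

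- Counted time in days 15 to 30: (1 − p)[m(e^(−14/m) − e^(−30/m)) − 16e^(−30/m)] = 0.92 × [10 × (0.2466 − 0.0498) − 16 × 0.0498] = 1.08 days.
- Probability of continuing: 0.92 × (1 − 0.0498) = 0.874.
- Counted time in continuing cycles: 0.92 × [98 × 0.9502 + 10 − 40 × 0.0498] = 93.0 days.
- Counted time in ending cycles: (1 − 0.874) × (98 + 14) = 14.1 days.
- Total: 107.1 days, so the share in days 15 to 30 is f = 1.08 / 107.1 = 1.0%.
- The rate is multiplied by about 1 − f × q, so it is understated by 1.0% × 0.3 = 0.3% to 1.0% × 0.9 = 0.9%.

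**4. What is not bias.** Against a 30-day tail for everyone, stoppers lose 0.126 × 16 = 2.0 days per cycle. That is 2.0 / (107.1 + 2.0) = 1.8% of person-time, and their events in that time go with it. Total event loss is (2.0 + 1.08 × 0.3) / 109.1 = 2.1% to (2.0 + 1.08 × 0.9) / 109.1 = 2.7%, but the 1.8 points from the shorter tail leave the rate unchanged.

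**5. Range.** The same formula with p = 0.08, supply of 28 to 100 days, mean gaps of 5 to 30 days and q of 0.5 to 1 gives f = 0.2% to 4.2% and rates understated by 0.1% to 4.2%. The top of the range is 28-day supply, 30-day mean gap and q = 1.

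**6. Between drugs.** If phenprocoumon gaps averaged 30 days and NOAC gaps 5 (purely illustrative), the NOAC hazard ratio would be multiplied by 1.007 (98-day supply, q = 0.5) to 1.037 (28-day supply, q = 1).

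With one tail for everyone, 14 or 30 days, the rate factor is 1 under constant hazard.

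**The case against.** The strongest reply has four parts.

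- **The clock conflict is a slip.** The discontinuation sentence reuses the term for the gap already defined in the same section. Read literally, it would make the days-of-supply rules and the phenprocoumon dose work pointless. This is probably right and lowers the practical risk. It does not remove the need to correct the only sentence that defines discontinuation.
- **A 30-day gap and a 14-day tail can coexist.** One decides whether an episode continues, the other how much exposure is credited after stopping. A reader might infer that the two numbers contradict each other. They do not. The defect is that membership of the risk set in days 15 to 30 turns on a later refill.
- **The protocol does not date discontinuation, and the SAP may.** The reading in which a stopper is censored on day 14 follows naturally from the tail applying in case of discontinuation, but it is an inference. If instead an event on day 20 counted because discontinuation was not yet established, stoppers' days 15 to 30 would still be missing from the denominator and rates would be overstated. Either way a common window is needed.
- **Other exposure assumptions matter more.** In the earlier study's table in Section 7, changing the phenprocoumon exposure definition moved mean follow-up for ischaemic stroke from 219.56 to 415.4 days and the hazard ratio from 0.84 to 1.02. This stands. That change was in the daily dose, so it is no measure of the present bias.

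**Conclusion.** The point holds, with a small effect. As naturally read, Section 9.3.1 makes at-risk status in days 15 to 30 depend on a future refill and loses events that prevent it. The understatement of rates is about 0.3% to 0.9% under the central assumptions and up to about 4% under extreme ones. All of these rest on refill patterns that the protocol does not give.

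Two stronger readings are not supported. A reader might take the whole 2% to 3% event loss as bias, but most of it is the shorter tail, whose person-time is removed too. A reader might also infer a known distortion against one drug, because phenprocoumon supply rests on a single median dose. The protocol gives no gap frequencies, a median overstates supply for some patients and understates it for others, and the personalised-dose sensitivity analysis already addresses that cause in part. A differential effect is possible but not shown.

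The clock wording is probably a slip. It should still be corrected, because taken literally it misclassifies every punctual refiller of a pack lasting more than 30 days in the persistence analysis and cuts that patient's follow-up short.

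**What to change.** In Section 9.3.1:

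1. Reword the discontinuation sentence so that the gap runs from the estimated end of supply, as in the gap sentence.
2. Use the same window after the end of supply for refillers and stoppers, both for at-risk time and for declaring discontinuation.
3. State the date assigned to discontinuation, so that follow-up, switching and persistence share one definition.
4. Add the other window length to the sensitivity analyses in Section 9.7.3.

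The cost is wording in the protocol and SAP, one parameter in the exposure program and one extra analysis run. No new data are needed. The downside is a slightly longer or shorter tail for some patients.
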